### Secondary Objectives

- 1.2 To assess the effect of finasteride on the stage and grade of carcinoma of the prostate at the time of diagnosis.
- 1.3 To assess the toxicity and side effects of finasteride when administered on a long-term basis.
- 1.4 To estimate the difference in the total and prostate-cancer specific mortality between men treated with finasteride and those treated with placebo.
- 1.5 To estimate the difference in incidence and severity of benign prostatic hyperplasia between men treated with finasteride and those treated with placebo.
- 1.6 To estimate the sensitivity, specificity and predictive values of digital rectal examination (DRE), PSA (Prostate Specific Antigen) and PSA + DRE as screening tests for the detection of prostate cancer, and to estimate the effect of long-term finasteride treatment on these screening parameters.
- 1.7 To assess the effect of long-term treatment with finasteride on the participants' self-report of urinary and sexual function symptoms and other Quality of Life dimensions.
- 1.8 To investigate whether dietary fat, assessed as intake of total fat, saturated fat and high fat foods, is associated with increased risk of prostate cancer (see Appendix 19.7 for related aims).
- 1.9 To assess the degree to which CAG trinucleotide repeat length is associated with an increased risk of prostate cancer (see Appendix 19.8 for related aims).

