## **10.0 CRITERIA FOR EVALUATION AND ENDPOINT DEFINITIONS**

The primary endpoint of this study is histologically proven presence/absence of carcinoma of the prostate after seven years.

- 10.1 Survival is defined as the period of time between Final Enrollment and death of any cause.
- 10.2 Prostate cancer-specific survival is defined as the period of time between Final Enrollment and death due to prostate cancer. For staging criteria, see Section 19.2.
- 10.3 Criteria for Estimation of Performance Status: At the First Visit participants will be graded according to the current Southwest Oncology Group grading scale:

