possible in the finasteride arm. Therefore the degree of medication adherence and contamination must be known when performing PSA assessments. The plan is to assess adherence/contamination prior to obtaining PSA specimens and to defer taking a PSA specimen in cases where there is evidence of nonadherence or contamination until there is sufficient adherence and lack of contamination. Thus, the participant is motivated to become adherent and not take open label finasteride. Also, meaningless PSA results are avoided. This strategy requires the following assumption, however:

**CRITICAL ASSUMPTION:** The procedures used to assess adherence in the individual participant at each visit where a PSA specimen is to be obtained are sufficiently sensitive and reliable to detect degrees of nonadherence affecting PSA level interpretation.

- 11.4 **SEVEN YEAR BIOPSY:** It is assumed that approximately 40% of the randomized participants will not have a prostate biopsy following seven years of study treatment and have not had a positive biopsy prior to seven years of treatment. Specifically, it is assumed there will be a 40% loss to biopsy based on the sum of 20% mortality, 15% lost to follow-up, and 5% biopsy refusals. The 20% mortality is based on an assumption that the median age at study entry will be 63 years, with the seven year U.S. (white) all-causes mortality for men that age assumed to be approximately 20%. The 15% lost to follow-up is based on experience with other prevention trials. The 5% biopsy refusal rate is based on the belief that participants who stay on the study drug for seven years will be motivated to find out whether or not they have prostate cancer.

**CRITICAL ASSUMPTION:** It is assumed that the factors affecting loss to biopsy will operate the same in both arms of the study so that the groups of participants who do not have biopsies (deaths, lost, refusal) will be comparable between the arms.

Conformity to the above assumption can be monitored by comparing between the arms the characteristics of the participants who do not have the seven year biopsy and the reason for not having the biopsy.

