- 11.14 **SECONDARY ANALYSES AND SECONDARY OBJECTIVES:** Beyond the analysis of the primary outcome described above, the probability of prostate cancer at seven years will be modeled using standard methods for categorical data, with explanatory variables including age, race, family history, gland size, laboratory data, etc. The probability of side-effects will be modeled using information on adherence (and other covariates).

Objective 1.2 (finasteride's effect on stage and grade) will be analyzed by comparing between the arms the grade and stage distribution of the incident cases. Data will come from pathology review of biopsy specimens. Standard categorical data analysis methods will be used.

Objectives 1.3, 1.4, 1.5, and 1.7 (toxicity, side-effects, mortality, BPH, and quality of life) will be analyzed by comparing between the arms the rates of events and magnitudes of effects. The data will come from reports of events, participant interviews, and side-effect and quality of life questionnaires. Standard categorical data methods, including methods for ordered categorical data will be used.

Objective 1.6 (finasteride's effect on screening modality) will require detailed pathology data as well as an analysis of the data generated from the procedures used to adjust PSA levels. Should finasteride prove to be efficacious in preventing prostate cancer then it will be important to be able to recommend to practitioners methods for monitoring for prostate cancer in those taking finasteride. Additional data addressing this issue may become available from trials of the use of finasteride in BPH.

Objective 1.8 (association of dietary fat and an increased risk of prostate cancer) will be approached as detailed in Appendix 19.7, which outlines methods of data collection and analysis.

Objective 1.9 (cohort study of CAG repeat length) will be approached as detailed in Appendix 19.8.

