#### **5.0 STATISTICAL CONSIDERATIONS**

The analyses of prostate cancer incidence and all-cause mortality following this extension will be similar to those conducted at the end of the PCPT, but will be augmented by additional endpoint data collected during the extension.

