### **Mortality**

To compare mortality in the control group with that in the intervention group, Kaplan-Meier curves with mortality as the endpoint will be constructed within each group. The curves will be compared using the logrank test at a significance level  $\alpha=0.05$ . This analysis will assume that individuals agreeing to continue with the short-term extension are representative of the population in terms of their mortality risk. As a check of this assumption we will compare participants who agree to continue with those who refuse in terms of their age, presence of prostate or any other cancer and other co-morbidities where information is available.

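### Section 11.14 names only categorical methods for mortality, which Section 10 defines as a survival time and Appendix 19.10 analyses with Kaplan-Meier and log-rank; no censoring rule is given for the end-of-trial analysis

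*Supplement*

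**What the plan says.** Objective 1.4 (Section 1.0) is "To estimate the difference in the total and prostate-cancer specific mortality between men treated with finasteride and those treated with placebo".

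Section 10.1: "Survival is defined as the period of time between Final Enrollment and death of any cause". Section 10.2: "Prostate cancer-specific survival is defined as the period of time between Final Enrollment and death due to prostate cancer". Neither gives a censoring rule, and 10.2 does not say how deaths from other causes are treated.

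Section 11.14 groups mortality with toxicity, BPH and quality of life. These objectives "will be analyzed by comparing between the arms the rates of events and magnitudes of effects", and the method is "Standard categorical data methods, including methods for ordered categorical data will be used". No survival method is named in that section.

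Section 11.4 assumes "there will be a 40% loss to biopsy based on the sum of 20% mortality, 15% lost to follow-up, and 5% biopsy refusals", takes these factors to act alike in both arms, and provides for monitoring of that assumption.

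Appendix 19.10, Section 5.0, states that the analysis of incidence and "all-cause mortality following this extension will be similar to those conducted at the end of the PCPT". Under Mortality it specifies that "Kaplan-Meier curves with mortality as the endpoint will be constructed within each group" and are compared by a log-rank test at the 0.05 level.

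**The concern.** The endpoint is a time, but the only method named for the end-of-trial analysis does not use times. A dead/alive table has no natural place for a man whose vital status is known for four years and then unknown. He must be counted as alive or left out, and Section 11.14 does not say which.

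Two things are at stake. Objective 1.4 is an estimation objective, and either coding misstates the seven-year risk. In addition, if loss should differ between arms, a proportion turns part of that difference into an apparent mortality effect, whose direction depends on a coding choice the plan leaves open. Meanwhile, Appendix 19.10 uses a method that needs neither coding and links it to the end-of-trial analysis, so the current protocol can be read two ways for one endpoint.

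**Working it through.** **The plan's own figures.** Loss to biopsy: 20% + 15% + 5% = 40%, leaving 0.60 × 9,000 = 5,400 per arm, as stated. The documents give no power figure for mortality. Section 11.12 shows how the plan handles another event outcome, coronary artery disease: 0.025 × 7 × 9,000 = 1,575 cases, or 17.5% of the arm, with nothing taken off for death or loss. A two-proportion calculation of 1,575 against 1,733 of 9,000 at one-sided 0.05 gives 91.9% power (stated 91.4%). A simple-proportion reading of Section 11.14 is therefore plausible, though not compelled.

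**Inputs.** From the documents: 9,000 per arm (Section 11.1); 20% seven-year mortality and 15% lost (Section 11.4). Assumed here: constant hazards; loss independent of death; all lost men have unknown vital status afterwards; a two-sided 5% test; every unequal-loss split; the hazard ratio of 0.90.

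**Formulas.** Death hazard λ = −ln(0.8)/7 = 0.0319 per year. The loss hazard μ is solved so that the fraction lost equals the target (μ = 0.0261 for 15%).

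- Observed dead share: D = λ/(λ+μ) × (1 − exp(−7(λ+μ)))
- Lost counted as alive: risk = D
- Lost dropped: risk = D/(1 − fraction lost)
- Person-time rate: D divided by (1 − exp(−7(λ+μ)))/(λ+μ), which equals λ whatever the loss

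**Equal 15% loss, no true effect.** D = 0.1834, so the risk reads 18.3% (alive) or 0.1834/0.85 = 21.6% (dropped), against 20%. Both arms move together: the ratio is 1.000 and the type I error 5.0%.

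**Equal 15% loss hazard, assumed hazard ratio 0.90.** True risks are 20% and 1 − 0.8^0.9 = 18.19%, a difference of 1.81 points and a ratio of 0.910. With lost men counted as alive, the difference is 1.66 points (1.66/1.81 = 0.92, about 8% smaller) and the ratio 0.909. With lost men dropped, the difference is 1.92 points (about 6% larger) and the ratio 0.911. The person-time rate ratio recovers 0.900. Power is 83.5% for the lost-as-alive proportions and 84.1% for log-rank, so little power is at issue.

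**Unequal loss, no true effect.**

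| Lost (arm 1 vs arm 2) | Ratio, lost = alive | Rejection | Ratio, lost dropped | Rejection |
|---|---|---|---|---|
| 15% vs 17% | 0.988 | 6.8% | 1.011 | 6.5% |
| 15% vs 18% | 0.981 | 9.2% | 1.017 | 8.5% |
| 13% vs 17% | 0.976 | 12.4% | 1.022 | 11.2% |
| 15% vs 20% | 0.969 | 17.1% | 1.029 | 15.3% |
| 12% vs 18% | 0.963 | 21.9% | 1.034 | about 19% |

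In the last row D is 0.1868 and 0.1800, a deficit of about 61 counted deaths (z = −1.18). The two codings point in opposite directions in every row. The person-time rate ratio is 1.000 throughout.

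**The case against.** The strongest reply is that this is a gap in wording with little practical consequence, and several parts of it stand.

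- A reader might infer that 15% loss by itself biases the comparison of deaths. It does not. Under the equal loss that Section 11.4 assumes and monitors, the null ratio is 1.000 and the test keeps its size.
- The unequal splits are not in the documents. A reader might also infer that side effects of finasteride will produce them. The documents give no differential loss rate, and stopping drug is not loss: Section 7.6e keeps men who are off treatment in twice-yearly follow-up, and Section 7.14d says participants are not dropped.
- The 15% is a component of loss to biopsy. Vital status may be known for many of these men, because deaths are an outcome on the Study Calendar and death certificates are submitted (Section 16.0). It is an upper-range figure for this purpose.
- Section 11.14 speaks of rates, which could mean person-time, and it sets no alpha for mortality. The rejection rates above suppose a test that the section does not spell out.
- Appendix 19.10 can be read as showing that a time-to-event analysis was intended all along.

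The last point does not close the gap. The appendix governs the analysis after the extension and does not amend Section 11.14, whose method sentence names categorical methods only. Monitoring of loss also comes with no stated fallback for the mortality analysis if the arms turn out to differ.

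**Conclusion.** The point holds as an inconsistency and an omission. Section 11.14 does not match the endpoint definitions in 10.1 and 10.2 or the method in Appendix 19.10. No censoring rule is given for all-cause mortality at the end of the trial, and no rule for other-cause deaths in prostate-cancer-specific mortality.

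Its size is modest. With simple proportions and equal uninformative loss, the harm is confined to estimation: an absolute risk off by about 1.6 points either way, and a risk difference about 8% too small if lost men are counted as alive. Only if loss differed by an assumed 2 to 6 points would the comparison itself be distorted, by a ratio of about 0.96 to 0.99 or 1.01 to 1.03 according to coding. These figures rest on constant hazards, 20% mortality in both arms under the null, and the full 15% having unknown vital status. The documents do not support saying that the planned mortality comparison is biased as it stands. Objective 1.4 is secondary, but because the remedy costs so little, the text should be put right.

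**What to change.** In Section 11.14, take mortality out of the sentence on categorical methods. State that all-cause mortality will be analysed from randomization with Kaplan-Meier curves and the log-rank test, censoring at last contact, in line with Section 10.1 and Appendix 19.10. For prostate-cancer-specific mortality, state how deaths from other causes are handled, for example by cause-specific hazards. Keep categorical and ordered categorical methods for graded symptoms and BPH severity, where they fit.

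The cost is wording and a little more analysis work, since deaths and contacts are already recorded at scheduled visits. The limit should be stated as well: the censored analysis removes the dependence on equal loss between arms but still relies on loss being uninformative about death.

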## **12.0 DISCIPLINE REVIEW**

### 12.1 Pathology Review

- a. All participants registered on this study who undergo any procedure which yields prostate tissue for diagnosis (e.g., prostate biopsy, transurethral resection of the prostate, radical prostatectomy, open prostatectomy, fine needle aspiration of the prostate, or pelvic lymphadenectomy) must undergo centralized pathology review.
- b. The materials from any of the above procedures are to be forwarded to the Core Laboratory within 30 days of the diagnostic/therapeutic procedure. Remaining tissue will be banked for future study.

**Detailed procedures are found in Appendix Section 19.4.**

## **13.0 REGISTRATION GUIDELINES**

Enrollment and randomization procedures are specified in the Study Manual.

## **14.0 DATA SUBMISSION SCHEDULE**

Detailed data submission procedures are found in the Study Manual.

## **15.0 SPECIAL INSTRUCTIONS**

- 15.1 Central Laboratory Facility (CLF): All PSA/DHT/Cholesterol determinations will be performed by Endocrine Sciences. Additional sera will be banked for future study. Detailed procedures are found in the Study Manual.
- 15.2 The Serum and Tissue Utilization Subcommittee will oversee the use of the serum and tissue banks. Detailed procedures are found in the Study Manual.

## **16.0 ETHICAL AND REGULATORY CONSIDERATIONS**

The following must be observed to comply with Food and Drug Administration regulations for the conduct and monitoring of clinical investigations; they also represent sound research practice:

### Informed Consent

The principles of informed consent are described by Federal Regulatory Guidelines (Federal Register Vol. 46, No. 17, January 27, 1981, part 50) and the Office for Protection from Research Risks Reports: Protection of Human Participants (Code of Federal Regulations 45 CFR 46). They must be followed to comply with FDA regulations for the conduct and monitoring of clinical investigations.

### Institutional Review

This study must be approved by an appropriate institutional review committee as defined by Federal Regulatory Guidelines (Ref. Federal Register Vol. 46, No. 17, January 27, 1981, part 56) and the Office for Protection from Research Risks Reports: Protection of Human Participants (Code of Federal Regulations 45 CFR 46).

### Drug Accountability

For each drug supplied for a study, an accountability ledger containing current and accurate inventory records covering receipt, dispensing, and the return of study drug supplies must be maintained. Drug supplies must be kept in a secure, limited access storage area under the recommended storage conditions. During the course of the study, the following information must be noted on the accountability ledger; the identification code of the participant to whom drug is dispensed, the date(s) and quantity of drug dispensed to the participant, and the date(s) and quantity of drug returned by the participant; participants should return empty containers to the investigator, with the return noted on the ledger. These Accountability Forms must be readily available for inspection and are open to FDA inspection at any time.

### Adverse Experiences

Any unexpected or serious adverse experience, if deemed drug related, must be reported within 24 hours to the Southwest Oncology Group Operations Office Adverse Drug Reaction (ADR) representative ([name]), who will obtain information on the ADR. Depending on the nature of the reaction, the ADR representative will advise further. See guidelines on next page. All deaths considered drug-related must be reported immediately to the ADR representative. On double-blinded studies, if the investigator must know what treatment the participant received to make therapeutic decisions, the code for that particular participant can be broken by telephoning the central unblinding number (see Study Manual for more details).

All adverse experiences must also be reported to the Institutional Review Board within 10 days and documentation of this report sent to the Southwest Oncology Group Operations Office.

All adverse experiences must also be recorded in the appropriate section of the case report form. The report should include, whenever possible, the investigator's written medical judgment as to relationship of the adverse experience to study medication(s) (i.e., "probable", "possible" or "unrelated").

GUIDELINES FOR REPORTING OF ADVERSE DRUG REACTIONS (ADRs)/ADVERSE EVENTS (AEs)  
OCCURRING WITH FINASTERIDE ON **SWOG-9217**

**WITHIN 24 HOURS OF NOTIFICATION OF THE REACTION**

**CALL THE OPERATIONS OFFICE AT [name]**

**WITHIN 10 DAYS, SEND TO THE OPERATIONS OFFICE**

- 1) **A COPY OF THE ADR REPORTING FORM**
- 2) **IRB NOTIFICATION DOCUMENTATION**
- 3) **COPIES OF ALL DATA RECORDS**

All Grades 3 - 5 Unknown Reactions and Grades 4 - 5 Known Reactions according to the Southwest Oncology Group Toxicity Criteria must be reported as ADRs/AEs. All hospital discharge summaries and death certificates will be submitted for evaluation.

**For grading reaction, see Southwest Oncology Group Toxicity Criteria, Section 19.0. Please do NOT use the NCI Common Toxicity Criteria version 2.X for toxicity or adverse event reporting.**

The ADR report should be documented on the Southwest Oncology Group ADR Form and mailed to the following address:

ATTN: ADR Program  
Southwest Oncology Group  
Operations Office  
[name]  
[name]

A list of all known toxicities can be found in either the Drug Information, Background or Informed Consent Form of the protocol.

New diagnoses of cancer, including prostate cancer, in PCPT participants need not be reported as adverse events. However, all diagnosis of cancer must be reported as assessment data in accordance with Section 9.0 and the Study Manual.

Reactions judged definitely not to be treatment related should not be reported. **However, a report shall be submitted if there is only a reasonable suspicion of drug effect.**

Copies of reports of all Grades 3 - 5 Unknown Reactions will be forwarded from the Operations Office to the FDA (using the guidelines provided in the Code of Federal Regulations 21 CFR 312.32), [name], Jr., M.D., DCPC and Merck Research Laboratory.

**Specific Adverse Event Reporting Guidelines for PCPT  
End-of-study Prostate Biopsies**

- Adverse events *related to biopsy* that should be reported:
  1. Bleeding requiring either hospitalization or transfusion
  2. Infection requiring antibiotic therapy
  3. Any hospital admission (include diagnosis and outcome in report)
  4. Death
- If any other biopsy-related event occurs that seems to meet the requirement for reporting according to the protocol adverse event guidelines, call the AE Specialist in the Operations Office [contact]) to discuss.

## **18.0 MASTER FORMS SET**

Forms and procedures are contained in the Study Manual.

A copy of the Model Informed Consent document is enclosed and must be reviewed and approved by the institutional IRB before placing a participant on study.

A copy of the Model Informed Consent document for the Participant Database is also enclosed and must be reviewed and approved by the institutional IRB before being presented to participants.

A copy of the Model Informed Consent document for the White Blood Cell and Plasma Collection Procedures is also enclosed (in **Section 19.9**) and must be reviewed and approved by the institutional IRB before being presented to the participants.

A copy of the Model Informed Consent document for the Extended Follow-Up is also enclosed (in **Section 19.10**) and must be reviewed and approved by the Institutional IRB before being presented to the participants.

## SOUTHWEST ONCOLOGY GROUP TOXICITY CRITERIA

1. Toxicity grade should reflect the most severe degree occurring during the evaluated period.
2. Toxicity grade = 5 if that toxicity caused or contributed to the death of the patient.
3. Do not code if the symptoms are certainly or most likely due to disease or other non-treatment cause.
4. If patient at baseline has Grade 1 or greater, do not code unless patient worsens due to toxicity. If there is worsening, code the level the patient increases to -- do NOT adjust for baseline.
5. Code all toxicities that apply, e.g., for a patient with pneumonitis, code pneumonitis as well as any pulmonary function codes which apply.
6. NCI codes for infection, pulmonary, neuro-sensory, neuro-cortical, neuro-cerebellar, neuro-constipation and skin will be calculated at the Statistical Center from the Southwest Oncology Group codes.
7. Note that for some toxicities certain grades are not defined and may not be coded.
8. Granulocytes/Bands refers to segmented neutrophils plus bands.

		GRADE				
Codes	Toxicity	0	1	2	3	4
HEMATOLOGIC						
HE0	WBC	4.0	3.0 - 3.9	2.0 - 2.9	1.0 - 1.9	< 1.0
HE1	PLT	LLN	75.0 - < LLN	50.0 - 74.9	25.0 - 49.9	< 25.0
HE2	Hgb	LLN	10.0 - < LLN	8.0 - 9.9	6.5 - 7.9	< 6.5
HE3	Granulocytes/ Bands	2.0	1.5 - 1.9	1.0 - 1.4	0.5 - 0.9	< 0.5
HE4	Lymphocytes	2.0	1.5 - 1.9	1.0 - 1.4	0.5 - 0.9	< 0.5
HE9	Hematologic- Other (specify)		mild	moderate	severe	life-threatening
CARDIAC						
CA0	Cardiac- Dysrhythmia	none	asymptomatic, transient requiring no therapy	recurrent or persistent, no therapy required	requires treatment	requires monitoring; or hypotension or ventricular tachycardia, or fibrillation
CA1	Cardiac- EF/CHF	none	asymptomatic, decline of resting ejection fraction by 20% of baseline value	asymptomatic, decline of resting ejection fraction by > 20% of baseline value	mild CHF, responsive to therapy	severe or refractory CHF
CA2	Cardiac- Ischemia	none	non-specific T-wave flattening	asymptomatic, ST and T wave changes suggesting ischemia	angina without evidence for infarction	acute myocardial infarction
CA3	Cardiac- Pericardial	none	asymptomatic effusion, no intervention required	pericarditis (rub, chest pain, ECG changes)	symptomatic effusion; drainage required	tamponade; drainage urgently required
CA9	Cardiac- Other (specify)	mild	moderate	severe	life-threatening	
CIRCULATORY						
CI0	Hypertension	none or no change	asymptomatic, transient increase by > 20mm Hg (D) or to > 150/100 if previously WNL. No treatment required	recurrent or persistent increase by > 20mm Hg (D) or to > 150/100 if previously WNL. No treatment required	requires therapy	hypertensive crisis
CI1	Hypotension	none or no change	changes requiring no therapy (including transient orthostatic hypotension)	requires fluid replacement or other therapy but not hospital- ization; or syncope	requires therapy and hospitalization; resolves within 48 hrs of stopping the agent	requires ther- apy and hos- pitalization for > 48 hrs after stopping the agent, or shock

Codes	Toxicity	GRADE				
		0	1	2	3	4
CI2	Phlebitis/ Thrombosis/ Embolism	none		superficial phlebitis (not local)	Deep vein thrombosis	major event (cerebral, hep- atic, pulmon- ary, other infar- ction) or pulmonary embolism
CI3	Edema	none	1+ or dependent in evening only	2+ or dependent throughout day	3+	4+, generalized anasarca
CI4	Veno-Occlusive Disease	none			yes	
CI9	Circulatory Other (specify)		mild	moderate	severe	life-threatening
CLOTTING						
CL0	Fibrinogen	LLN	0.99 - 0.75 x LLN	0.74 - 0.50 x LLN	0.49 - 0.25 x LLN	0.24 x LLN
CL1	Prothrombin Time	ULN	1.01 - 1.25 x ULN	1.26 - 1.50 x ULN	1.51 - 2.00 x ULN	> 2.00 x ULN
CL2	Partial Thrombo- plastin Time	ULN	1.01 - 1.66 x ULN	1.67 - 2.33 x ULN	2.34 - 3.00 x ULN	> 3.00 x ULN
CL9	Clotting - Other (specify)		mild	moderate	severe	life-threatening
DERMATOLOGIC						
SK0	Local	none	pain, erythema or itching	pain and swelling, with inflammation or phlebitis	ulceration or necrosis	plastic surgery indicated
SK1	Skin Rash/Urticaria	none	asymptomatic scattered macular or papular eruption	scattered eruption with pruritus or other symptoms (also code Skin Ulceration or Skin Necrosis if applicable)	generalized symptomatic eruption	exfoliative dermatitis
DE6	Pruritus	none	mild and localized; relieved spontaneously or by local measures	intense or wide- spread; relieved spontaneously or by systemic measures	intense or widespread; incompletely re- lieved any measure	
SK2	Blistering	none	asymptomatic eruption	limited eruption, symptomatic	generalized symptomatic eruption	
(also code Desquamation, Skin Ulceration or Skin Necrosis if applicable)						
SK3	Erythema	none	asymptomatic	erythema with pruritus or tenderness		
SK4	Erythema in RT Field	(same definition as Erythema)				
SK5	Desquamation	normal	peeling, dry desquamation	patchy moist desquamation	confluent moist desquamation other than skin folds	
(also code Skin Ulceration or Skin Necrosis if applicable)						
SK6	Desquamation in RT Field	(same definition as Desquamation)				
SK7	Skin Necrosis (non-local)	none				yes
SK8	Skin Ulceration (non-local)	none				yes but 2 weeks
SK9	Chronic Skin Change	none		telangiectatic changes or atrophy	fibrosis, contrac- tures or scarring	non-healing ulcers > 2 weeks
DE0	Pigmentation Changes	none	mild	pronounced		
DE1	Photosensitivity	normal		yes		
(also code Erythema, Blistering or Desquamation if applicable)						
DE2	Dry Skin	normal	controlled with emollients	not controlled with emollients		
DE3	Hand-foot Syndrome	no	-	yes		
(also grade appropriate dermatologic phenomena)						
DE4	Granuloma	no	-	yes		
(also grade Pain if it applies)						

		GRADE				
Codes	Toxicity	0	1	2	3	4
DE5	Skin Yellowing	none	present on close exam	prominent (seen at a distance)		
DE9	Dermatologic- Other (specify)		mild	moderate	severe	life-threatening
ENDOCRINE						
EN0	Impotence/ Libido	normal	decrease in normal function		absence of function	
EN1	Sterility				yes	
EN2	Gynecomastia	normal	mild	pronounced or painful		
EN3	Hot flashes	none	mild or < 1/day	moderate and 1/day	frequent and interferes with normal function	
EN4	Menses: At time off study, did pt. experience -	normal menses throughout	occasionally irregular or lengthened interval, but continuing	very irregular, but continuing	amenorrhea, no menses for at least 6 mo	
EN5	Cushingoid	normal	mild	pronounced		
EN6	Erectile Impotence	nothing wrong	mild (erections impaired but satisfactory)	moderate (erections impaired, unsatisfactory for intercourse)	severe (no erections)	
EN9	Endocrine- Other (specify)		mild	moderate	severe	life-threatening
EYE						
EY0	Conjunctivitis/ Keratitis	none	erythema or chemosis not requiring steroids or antibiotics	requires treatment with steroids or antibiotics (also code vision if applicable)	corneal ulceration or visible opacification	
EY1	Dry eye	normal		requires artificial tears		requires enucleation
EY2	Glaucoma	no change			yes	
EY9	Eye- Other (specify)		mild	moderate	severe	life-threatening
FLU-LIKE SYMPTOMS						
FL0	Fever in Absence of Infection	none	37.1 - 38.0°C 98.7 - 100.4°F	38.1 - 40.0°C 100.5 - 104.0°F	> 40.0°C > 104.0°F for less than 24 hours	> 40.0° C (104.0°F) for more than 24 hours or fever accompanied by hypotension
FL1	Chills	none	mild or brief	pronounced and prolonged		
FL2	Myalgia/ Arthralgia	normal	mild	decrease in ability to move	disabled	
FL3	Sweats	normal	mild and occasional	frequent or drenching		
FL4	Facial Flushing	normal	yes			
FL9	Other Flu-Like Symptoms (specify)		mild	moderate	severe	life-threatening
GASTROINTESTINAL						
GI0	Nausea	none	able to eat reasonable intake	intake significantly decreased but can eat	no significant intake	
GI1	Vomiting	none	1 episode in 24 hrs	2 - 5 episodes in 24 hrs	6 - 10 episodes in 24 hrs	> 10 episodes in 24 hrs or requiring parenteral support
GI2	Diarrhea	none	increase of 2 - 3 stools/day over pretreatment	increase of 4 - 6 stools/day, or nocturnal stools or moderate cramping	increase of 7 - 9 stools/day, or incontinence, or severe cramping	increase of 10 stools/day, grossly bloody diarrhea or need for parenteral support

Codes	Toxicity	GRADE				
		0	1	2	3	4
GI3	Constipation	none	stool softener required	laxatives required	obstipation with enema, manual or surgical evacuation required	
GI4	Ileus	no			yes, < 96 hrs	yes, 96 hrs
GI8	Anal Incontinence	no	resolves without treatment (< 1 wk); self-limited illness	controlled by diet or generic antidiarrheal	medically uncontrollable or controlled by surgery	
GI5	Gastritis/ Ulcer	no	antacid	requires vigorous medical management or non-surgical treatment	uncontrolled by medical management; requires surgery for GI ulceration	perforation or bleeding
GA0	Pancreatitis	no			inflammatory response confined to pancreas; self-limited	shock; pancreatic hemorrhage or necrosis;
GI6	Small Bowel Obstruction	no		intermittent, no intervention	illness requires intervention	chronic illness requires operation
GI7	Intestinal Fistula	no			yes	
GI9	GI - Other (specify)		mild	moderate	severe	life-threatening
HEMORRHAGE						
HM0	Hemorrhage (clinical)	none	mild, no transfusion	gross, 1-2 units transfusion per episode	gross, 3-4 units transfusion per episode	massive, > 4 units transfusion per episode
HM2	Epistaxis	none	self-limited, controlled by conservative measures		cauterization, artery ligation or packing of posterior nasal cavity; requires hospitalization	
HM1	Rectal Bleeding	none		intermittent, no steroids	requires steroids	requires transfusion (code hemorrhage also)
HM3	Vaginal bleeding	normal	prolonged, increased frequency or profuse but self-limited; no or minimal local tx required	medical therapy required	uterine curettage	requires transfusion (code hemorrhage also)
IMMUNOLOGICAL						
IM0	Allergy (also code rash if it applies)	none	transient rash, drug fever < 38° C, 100.4° F	urticaria, drug fever 38° C, 100.4° F, mild bronchospasm	serum sickness, bronchospasm, requires parenteral meds	anaphylaxis
IM1	Immunosensitivity Reaction	none	(definitions will be agent specific)			
IM2	Acute GVHD	none	I	II	III	IV
IM9	Immuno - Other (specify)		mild	moderate	severe	life-threatening
INFECTION						
IN0	Other Infection (specify site)	none	no active treatment (e.g., viral syndromes)	PO antibiotics	IV antibiotic or antifungal or hospitalization	life-threatening e.g., septic shock
IN1	Respiratory Infection	(Same definitions as Other Infection)				
IN2	Urinary tract Infection	(Same definitions as Other Infection)				

Codes	Toxicity	GRADE				
		0	1	2	3	4
IN3	Wound Infection	no		PO antibiotics	IV antibiotic or antifungal or surgical intervention	life-threatening e.g., septic shock
IN5	Infection at Catheter Site	no		Local care and PO antibiotics; local infection	Febrile illness; IV antibiotic or antifungal or surgical intervention	life-threatening e.g., septic shock
IN4	Abscess	no ( also code Infection if it applies )		yes		
LIVER						
LI0	Bilirubin	ULN		< 1.5 x ULN	1.5 - 3.0 x ULN	> 3.0 x ULN
LI1	Transaminase (SGOT, SGPT)	ULN	2.5 x ULN	2.6 - 5.0 x ULN	5.1 - 20.0 x ULN	> 20.0 x ULN
LI2	Alk Phos or 5' nucleotidase	ULN	2.5 x ULN	2.6 - 5.0 x ULN	5.1 - 20.0 x ULN	> 20.0 x ULN
LI3	Liver - Clinical	no change from baseline			precoma	hepatic coma
LI9	Liver - Other (specify)		mild	moderate	severe	life-threatening
LUNG						
LU0	Dyspnea	no change		SOB on significant exertion	dyspnea at normal level of activity	dyspnea at rest
LU1	pO 2 /pCO 2	no change or pO 2 > 85 and pCO 2 40	pO 2 > 70 and pCO 2 50, but not Grade 0	pO 2 > 60 and pCO 2 60 but not Grade 0-1	pO 2 > 50 and pCO 2 70, but not Grade 0 - 2	pO 2 50 or pCO 2 > 70
LU2	CO Diffusion Capacity	> 90% of pretreatment value	decrease to 76 - 90% of pretreatment	decrease to 51 - 75% of pretreatment	decrease to 26 - 50% of pretreatment	decrease to 25% of pretreatment
LU3	Pulmonary Fibrosis	normal	radiographic changes, no symptoms		changes with symptoms (also code symptoms)	
LU4	Pulmonary Edema	none			radiographic changes and diuretics required	requires intubation
LU5	Pneumonitis (non-infectious)/ Pulmonary Effusions/ Infiltrates	normal	radiographic changes, symptoms do not require steroids	steroids required or tap of effusion	oxygen required	requires assisted ventilation
LU6	Cough	no change	mild, relieved by OTC meds	requires narcotic antitussive	uncontrolled coughing spasms	
LU9	Lung -Other (specify)		mild	moderate	severe	life-threatening
METABOLIC						
ME0	Hyponatremia	no change or > 135	131-135	126-130	121-125	120 (also code any CNS toxicities which apply)
ME1	Hypokalemia	no change or > 3.5	3.1-3.5	2.6-3.0	2.1-2.5	2.0 (also code Cardiac if applicable)
ME2	Hyperglycemia	< 116	116-160	161-250	251-500	> 500 or ketoacidosis
ME3	Hypoglycemia	> 64	55-64	40-54	30-39	< 30
ME4	Amylase	ULN	< 1.5 x ULN	1.5-2.0 x ULN	2.1-5.0 x ULN	> 5.0 x ULN
ME5	Hypercalcemia	< 10.6	10.6-11.5	11.6-12.5	12.6-13.5	> 13.5
ME6	Hypocalcemia	> 8.4	8.4-7.8	7.7-7.0	6.9-6.1	6.0
ME7	Hypomagnesemia	> 1.4	1.4-1.2	1.1-0.9	0.8-0.6	0.5
ME8	Hypothyroidism	no	TSH elevated, asymptomatic, no therapy given	Symptomatic; thyroid hormone replacement therapy given	Patient hospitalized for manifestations of hypothyroidism	Myxedema coma
ME9	Metabolic- Other (Specify)		mild	moderate	severe	life-threatening

Codes	Toxicity	GRADE				
		0	1	2	3	4
MUCOSAL						
MU0	Stomatitis	none	painless ulcers, erythema or mild soreness	painful erythema, edema, or ulcers, but can eat solids	painful erythema edema, or ulcers and cannot eat solids	requires parenteral or enteral support
MU1	Pharynx/ Esophagitis	none	painless ulcers, erythema, mild soreness or mild dysphagia	painful erythema, edema, or ulcers or moderate dysphagia but can eat solids	cannot eat solids	requires parenteral or enteral support or complete obstruction or perforation
MU2	Vaginitis	none	(same definition as Other Mucositis)			
MU3	Pseudomembranes	none	yes			
MU9	Other Mucositis (specify site)	none	erythema, or mild pain not requiring treatment	patchy & produces serosanguinous discharge or requires non-narcotic for pain	confluent fibrinous mucositis or requires narcotic for pain or ulceration	necrosis
NEUROLOGIC/NEUROCENTRAL						
NC0	Disorientation	normal	confusion or disorientation, easily reoriented, some change in activity	confusion or disorientation requiring supervision	confusion or disorientation requiring institutionalization; or hallucinations	
